6	Primary Outcome Measure	Count of HCS residents who are Medicaid enrollees with OUD who are screened, diagnosed, and treated for hepatitis C
7	Population Size Adjustment	Medicaid beneficiaries during the time period

1	Definition Number	2.16
2	Definition Name	Number of newly diagnosed HIV cases
3	Population	All residents
4	Data Sources	State-specific registry for HIV/AIDS reporting; funding provided by CDC to state health departments for surveillance ( http://www.cdc.gov/hiv/library/reports/surveillance/ )
5	Other Available Data for Additional or State-Specific Analyses	Medicaid claims data
6	Primary Outcome Measure	Count of newly diagnosed cases of HIV
7	Population Size Adjustment	The population size estimate for each HCS community will be the mid-year population estimate as of July 1 for the year under surveillance

	Definition Number	2.17
2	Definition Name	Number of opioid-related overdoses treated in EDs and captured by syndromic surveillance data
3	Population	This is a population measure and would refer to the count in the local community; thus, all demographic groups would be included
4	Data Sources	Syndromic surveillance records (accessed via CDC's NSSP-ESSENCE application or other state-based platforms)
5	Other Available Data for Additional or State-Specific Analyses	N/A
6	Primary Outcome Measure	Number of opioid-related overdoses treated in EDs in the HCS community

7	Population Size Adjustment	Mid-year population estimates
----------	-----------------------------------	-------------------------------

1	Definition Number	2.18
2	Definition Name	Number of new acute opioid prescriptions limited to a 7-day supply
3	Population	All residents
4	Data Sources	Prescription drug monitoring program; census data for population estimates
5	Other Available Data for Additional or State-Specific Analyses	Claims (Medicaid in Kentucky and Ohio; all-payer in Massachusetts and New York—these are inferior to Prescription Monitoring Program (PMP) because they lack cash payments but would allow for removal of patients with cancer or on hospice care)
6	Primary Outcome Measure	Count of individuals with a new opioid prescription (45-day washout period preceding opioid prescription with no opioids) with a supply for $\leq 7$ days
7	Population Size Adjustment	The population size estimate for each HCS community will be the mid-year population estimate as of July 1 for the year under surveillance

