#### **9.4.3 Analysis of the Secondary Outcomes**

As with the primary outcome, secondary and structural outcomes will be modeled using an ITT approach as described above. The models will include trial arm as the main independent variable and will control for the following covariates: the RS (i.e., Kentucky, Massachusetts, New York, or Ohio), the rural/urban status of the community, baseline opioid overdose death rate, and the observed baseline level of the particular secondary outcome for the community. The secondary outcomes related to H2–H4 in Section 9.1 are counts or rates; therefore, a marginal negative binomial regression model estimated using GEE will be utilized to analyze the count outcomes, as with the primary analysis. For those outcomes that involve a rate, the implied denominator in the county during the 12-month parallel-arm trial period will be utilized to offset the model, such that the outcome is interpreted as a rate, and differences between treatment assignments would be rate ratios. A model-based approach will be used for hypothesis testing, as described in the primary analysis.

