6	Primary Outcome Measure	Individuals who maintained continual methadone MOUD for 6 months in the measurement period. Continuous treatment is calculated based on days' supply and dosage, and an individual can have a gap of no more than 7 days' treatment to be considered in continual treatment.
7	Population Size Adjustment	Medicaid enrollees with a diagnosis of OUD and a methadone claim during the first half of the measurement period—allowing for a full 6 months of measurement to occur after the initial claim

1	Definition Number	2.7.3
2	Definition Name	Number of individuals receiving naltrexone retained beyond 6 months
3	Population	Medicaid beneficiaries
4	Data Sources	Medicaid beneficiaries
5	Other Available Data for Additional or State-Specific Analyses	All-payer data in Massachusetts
6	Primary Outcome Measure	Individuals who maintained continual naltrexone MOUD for 6 months in the measurement period. Continuous treatment is calculated based on days' supply and dosage, and an individual can have a gap of no more than 7 days' treatment to be considered in continual treatment.
7	Population Size Adjustment	Medicaid enrollees with a diagnosis of OUD and a naltrexone claim during the first half of the measurement period—allowing for a full 6 months of measurement to occur after the initial claim

1	Definition Number	2.7.4
2	Definition Name	Number of individuals with MOUD retained in treatment beyond 6 months
3	Population	Medicaid
4	Data Sources	Medicaid administrative data
5	Other Available Data for Additional or State-Specific Analyses	All-payer claims in Massachusetts; BSAS in Massachusetts
6	Primary Outcome Measure	Individuals who, by (1) prescription MOUD, (2) office-administered MOUD, or (3) a combination of both, maintained continual MOUD for 6 months in the measurement period.

		Continuous treatment is calculated based on days' supply and dosage, and an individual can have a gap of no more than 7 days' treatment to be considered in continual treatment.
7	Population Size Adjustment	Medicaid enrollees with an OUD diagnosis, an MOUD claim during the measurement period, and continuous eligibility for 6 months after the first MOUD, concluding before the end of the measurement period

1	Definition Number	2.7.5

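### Six-month methadone and naltrexone retention (outcomes 2.7.2 and 2.7.3) carry no Medicaid eligibility condition, unlike 2.7.4, so some coverage lapses are counted as non-retention

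*Protocol*

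**What the plan says.** Protocol section 12.1.2 defines three six-month retention outcomes that Table 2 sources to Medicaid claims and eligibility files.

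- **2.7.2, methadone.** Numerator: "Individuals who maintained continual methadone MOUD for 6 months in the measurement period". Denominator: "Medicaid enrollees with a diagnosis of OUD and a methadone claim during the first half of the measurement period", with the stated purpose of "allowing for a full 6 months of measurement to occur after the initial claim".
- **2.7.3, naltrexone.** Numerator: "Individuals who maintained continual naltrexone MOUD for 6 months in the measurement period". Denominator: "Medicaid enrollees with a diagnosis of OUD and a naltrexone claim during the first half of the measurement period", with the same stated purpose.
- **2.7.4, any MOUD.** The denominator asks for an OUD diagnosis, an MOUD claim in the period and "continuous eligibility for 6 months after the first MOUD, concluding before the end of the measurement period".

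All three use one continuity rule: "an individual can have a gap of no more than 7 days' treatment to be considered in continual treatment". For secondary outcomes that involve a rate, Protocol section 9.4.3 says that "the implied denominator in the county during the 12-month parallel-arm trial period will be utilized to offset the model". Table 2 attaches no hypothesis to any of the three. The SAP defines only the opioid overdose death outcome and sets no rule for these measures.

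**The concern.** A first-half start leaves six months on the calendar. It does not ensure that the person can be seen for six months. Once Medicaid coverage ends, treatment paid for in another way produces no Medicaid claim, so continued treatment and stopped treatment look the same. Under 2.7.2 and 2.7.3 that person stays in the denominator and may be unable to enter the numerator. Under 2.7.4 the same person is left out.

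Two things are at stake. Reported methadone and naltrexone retention can be too low, and it follows a different observation rule from the all-MOUD figure reported beside it. In addition, where the denominator serves as the model offset, any difference between waves in loss of coverage goes straight into the rate ratio.

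**Working it through.** The plan states no retention rate, lapse rate or power for these outcomes, so there is no figure to reproduce. The check is a comparison of the definitions, followed by an illustration under stated assumptions.

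**Step 1. Is eligibility the operative difference?** In a 12-month period, requiring the six eligible months to finish before the period ends already forces a first-half start in 2.7.4. Apart from drug scope, the continuous-eligibility condition is therefore what separates its denominator from those of 2.7.2 and 2.7.3. Outcomes 2.5.4 and 2.7.5 also allow for enrolment, by using member-months.

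**Step 2. Which lapses matter?** The numerators ask for six continual months within the measurement period, not for the six months that follow the start of treatment.

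- A lapse after six completed months: still retained.
- An early lapse, then re-enrolment in time for a six-month run: still retained.
- A lapse covered by days' supply, or leaving a gap of 7 days or less: still retained.
- A lapse that leaves more than 7 days without observed supply and prevents any observed six-month run: not retained, even if treatment continued under another payer.

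Only the last case is misclassified.

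**Step 3. Size within one wave.** Let R be true retention, L the share of the denominator with a lapse of the last kind, and r the true retention among those people.

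- Measured retention = R − L × r. The shortfall is L × r, so it is at most L in absolute terms.
- If lapse is independent of retention, r = R and measured retention = R × (1 − L).

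With R = 60% and L assumed:

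- L = 5%: 0.60 × 0.95 = 0.57
- L = 10%: 0.60 × 0.90 = 0.54
- L = 20%: 0.60 × 0.80 = 0.48

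If those who lapse had all stopped treatment already, r = 0 and the shortfall is nil.

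**Step 4. Size between waves.** With no true effect and independence in both waves, the Wave 1/Wave 2 ratio = (1 − L1)/(1 − L2).

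- 10% vs 10%: 0.90/0.90 = 1.00
- 15% vs 10%: 0.85/0.90 = 0.944
- 20% vs 10%: 0.80/0.90 = 0.889
- 5% vs 10%: 0.95/0.90 = 1.056
- 10% vs 20%: 0.90/0.80 = 1.125

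**Step 5. What the 2.7.4 rule does.** It gives (R − L × r)/(1 − L). Under independence this returns R: 0.54/0.90 = 0.60. If r = 0 it gives 0.60/0.90 = 0.667, which is above the true 60%, because people who had stopped have been removed. When those who lapse are retained no more often than others, the two denominators bracket the true value. That is the reason to report both.

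**The case against.** Keeping every starter in the denominator is a defensible choice. Six months of eligibility is a post-treatment condition: death ends eligibility, so early deaths would leave the denominator, which is awkward in a trial whose primary outcome is overdose death. If the intervention changes survival or coverage, the restriction itself selects differently by wave. This stands, and the fix has to deal with it.

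The Appendix A rows may also be incomplete. Protocol section 10.1.8.1 describes them as brief, and SAP section 6.1 cites a separate technical specification (for outcome 1) that is not available here. An enrolment rule could be written there. If so, the protocol rows should state it.

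Other payer sources reduce the problem only in part. For methadone, Appendix A lists all-payer, Ohio mental health agency or Massachusetts addiction-services data in three states; for naltrexone, all-payer data in Massachusetts alone. All of these are reserved for additional or state-specific analyses.

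A reader might infer three stronger things, none of which the documents support:

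- **That any lapse counts as non-retention.** Step 2 of the working shows that several kinds of lapse do not.
- **That the bias runs against the intervention, because the CTH reaches people in unstable settings.** No section reports lapse rates or a difference by wave. Equal lapse leaves the ratio at 1.00, and more lapse in Wave 2 would favour Wave 1.
- **That the missing condition is why the drug-specific figures cannot be reconciled with 2.7.4.** They would not add up in any case. 2.7.4 covers any MOUD, so people who switch drugs can be retained there only, and 2.7.1 uses prescription-monitoring data with a general-population denominator.

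**Conclusion.** The inconsistency holds on the protocol text, and nothing else in the protocol or SAP closes it. Followed as written, 2.7.2 and 2.7.3 score as not retained some people whose treatment simply cannot be seen.

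Retention is understated by no more than the lapse share, or by 6 percentage points from a true 60% at an assumed 10% lapse. That example assumes that lapse is independent of retention, and it shrinks if those who lapse have mostly stopped already. Comparison between waves is affected only if lapse differs by wave, and the documents give no basis for a direction.

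These are other secondary outcomes outside H1 to H4, so severity is minor. The change is still worth making, since the protocol already contains the rule and the data source.

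**What to change.** 1. In the Population Size Adjustment rows of 2.7.2 and 2.7.3, add the 2.7.4 condition: continuous Medicaid eligibility for six months after the first methadone (or naltrexone) claim, ending before the measurement period closes. Restrict the numerator to the same people.
2. Where death can be identified, count people who die within those six months as not retained instead of excluding them.
3. Report the current denominator as a sensitivity analysis. The evaluation period ended in June 2022, so if results already exist, label the change as post hoc and show both versions.
4. If the technical specification already applies an enrolment rule, state that rule in Appendix A.

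The cost is two definition rows and a re-run with eligibility files that Table 2 already lists. The price is a smaller denominator selected on a post-treatment condition, which 2.7.4 already accepts.

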N/A	Number of individuals linked to MOUD after release from prison	2.10	Medicaid administrative data, including claims and eligibility files linked to incarcerated individual files from state departments of corrections
N/A	Number of individuals provided MOUD while in jail	2.11	Primary data collection—survey ( Justice Community Opioid Innovation Network [JCOIN] and HCS Annual Jail Survey )
N/A	Number of individuals linked to MOUD after an opioid-related ED visit	2.12	Medicaid administrative data, including claims and eligibility files
N/A	Number of individuals with OUD who are screened, diagnosed, and treated for hepatitis C	2.15	Medicaid administrative data, including claims and eligibility files
N/A	Number of newly diagnosed HIV cases	2.16	State registry for HIV/AIDS reporting
N/A	Number of opioid-related overdoses treated in EDs and captured by syndromic surveillance data	2.17	Syndromic surveillance records (accessed via the Centers for Disease Control and Prevention's National Syndromic Surveillance Program Electronic Surveillance System for the Early Notification of Community-based Epidemics (NSSP-ESSENCE) application or other state-based platforms)

Hypothesis	Associated Outcomes	Appendix A Reference Number	Data Source
N/A	Number of new acute opioid prescriptions limited to a 7-day supply	2.18	Prescription drug monitoring program
N/A	Opioid prescriptions from multiple prescribers or pharmacies	3.1	Prescription drug monitoring programs
N/A	Number of providers with a waiver under the Drug Addiction Treatment Act of 2000 (DATA 2000)	3.2	U.S. Drug Enforcement Administration's (DEA) Active Controlled Substances Act (CSA) Registrants Database
N/A	Number of providers with a DATA 2000 waiver who actively prescribe buprenorphine products that are FDA approved for OUD	3.3	DEA's Active CSA Registrants Database linked to prescription drug monitoring program data
N/A	Number of providers who actively prescribe buprenorphine products that are FDA approved for OUD	3.4	Prescription Drug Monitoring Program (PDMP) data
N/A	Number of jails initiating and linking people to MOUD	3.5	Primary data collection—survey ( Justice Community Opioid Innovation Network [JCOIN] and HCS Annual Jail Survey )
N/A	Number of take-back drug drop boxes and events	3.8	State administrative data and DEA's Active CSA Registrants Database
N/A	Number of ED visits for BH (count visits)	4.1.1	Medicaid administrative data, including claims and eligibility files

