7	Population Size Adjustment	Mid-year population estimate

1	Definition Number	2.9
2	Definition Name	Number of individuals linked to MOUD after opioid overdose
3	Population	Medicaid beneficiaries
4	Data Sources	Medicaid claims
5	Other Available Data for Additional or State-Specific Analyses	All-payer claims in Massachusetts and New York; Ohio can combine claims from Medicaid and OhioMHAS; BSAS in Massachusetts; prescription drug monitoring programs; EMS and hospital discharge data for Massachusetts
6	Primary Outcome Measure	2.9.1.: Count of individuals with $\geq 1$ claim for naltrexone, methadone maintenance treatment, or buprenorphine within 30 days of ED or inpatient discharge 2.9.2: Count of overdose events with $\geq 1$ claim for naltrexone, methadone maintenance treatment, or buprenorphine within 30 days of ED or inpatient discharge

7	Population Size Adjustment	2.9.1: Number of full-benefit Medicaid enrollees with an opioid overdose 2.9.2: Total number of opioid overdose events among full-benefit Medicaid enrollees
---	-----------------------------------	---

1	Definition Number	2.10
2	Definition Name	Number of individuals linked to MOUD after release from prison
3	Population	Imprisoned inmates released to HCS communities
4	Data Sources	State departments of corrections linked to Medicaid claims
5	Other Available Data for Additional or State-Specific Analyses	Departments of corrections data linked to all-payer claims, where available; OASAS in New York; BSAS in Massachusetts; prescription drug monitoring program in Massachusetts
6	Primary Outcome Measure	Number of individuals who reside in HCS communities who receive a first dose of MOUD within 2 and 4 weeks of release from prison as identified by Medicaid claims
7	Population Size Adjustment	Imprisoned inmates released to HCS communities

1	Definition Number	2.11
2	Definition Name	Number of individuals provided MOUD while in jail
3	Population	Jailed (pre-trial and sentenced) inmates at jails associated with each HCS community (if more than one, limit to top three jails)
4	Data Sources	Survey of jails associated with each HCS community

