5	Other Available Data for Additional or State-Specific Analyses	Linkage of Massachusetts jail releases to the prescription drug monitoring program in Massachusetts; all-payer claims data and BSAS data
6	Primary Outcome Measure	Number of individuals who received MOUD in community jails
7	Population Size Adjustment	Number of individuals were offenders in community jails

1	Definition Number	2.12
2	Definition Name	Number of individuals linked to MOUD after an opioid-related ED visit
3	Population	Medicaid beneficiaries
4	Data Sources	Medicaid claims
5	Other Available Data for Additional or State-Specific Analyses	All-payer claims in Massachusetts and New York; Ohio can combine claims from Medicaid and OhioMHAS; hospital/ED discharge data from Massachusetts; prescription drug monitoring data from Massachusetts; BSAS data from Massachusetts
6	Primary Outcome Measure	≥1 claim for naltrexone, methadone maintenance treatment, or buprenorphine within 30 days of ED or inpatient discharge
7	Population Size Adjustment	Medicaid beneficiaries with an opioid-related ED visit during the relevant study period

1	Definition Number	2.13
2	Definition Name	Incidents of high-risk opioid prescribing
3	Population	All residents
4	Data Sources	Prescription drug monitoring program data
5	Other Available Data for Additional or State-Specific Analyses	Claims (Medicaid in Kentucky; all-payer in Massachusetts and New York; combined Medicaid/OhioMHAS in Ohio)
6	Primary Outcome Measure	Count of individuals with one or more of the following during the 12-month study period, and not in a prior specified time window (3 months):  Risk of continued opioid use (new opioid episode lasting at least 31 days)  Initiating opioid treatment with an extended-release or long-acting opioid  Incident high dosage (average $\geq$ 90 mg morphine per day)  Incident overlapping opioid and benzodiazepine for $\geq$ 30 days (Measures A–D will be tracked separately and aggregated for the H4 analysis to a total count of unique individuals during the 12-month measurement period)
7	Population Size Adjustment	The population size estimate for each HCS community will be the mid-year population estimate as of July 1 for the year under surveillance

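### Outcome 2.10 divides a Medicaid-only count of MOUD linkage by everyone released from prison, so the reported linkage rate is too low by roughly the unenrolled share

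*Protocol*

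**What the plan says.** Protocol Appendix A, section 12.1.2, gives outcome 2.10 the following parts:

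- **Numerator:** residents of HCS communities who receive a first MOUD dose "within 2 and 4 weeks of release from prison as identified by Medicaid claims".
- **Population and Population Size Adjustment:** the same words in both rows, "Imprisoned inmates released to HCS communities". Neither row mentions Medicaid.
- **Data source:** "State departments of corrections linked to Medicaid claims". Protocol Table 2 is fuller: "Medicaid administrative data, including claims and eligibility files linked to incarcerated individual files from state departments of corrections".
- **Other sources:** "Departments of corrections data linked to all-payer claims, where available", the New York and Massachusetts state substance-use agency data (OASAS and BSAS) and the Massachusetts prescription drug monitoring program (PDMP). All of these sit in the row for additional or state-specific analyses.

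On use of the denominator, Protocol 9.4.3 says that for outcomes involving a rate "the implied denominator in the county during the 12-month parallel-arm trial period will be utilized to offset the model", and that the arms are then compared by rate ratios.

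The two neighbouring linkage outcomes are built differently. For linkage after overdose the denominator is "2.9.1: Number of full-benefit Medicaid enrollees with an opioid overdose". For linkage after an emergency department visit it is "Medicaid beneficiaries with an opioid-related ED visit during the relevant study period".

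**The concern.** The numerator and denominator of 2.10 come from different populations. The numerator can include only people whose MOUD generates a Medicaid claim. The denominator is a corrections count of everyone released to the community. Someone who leaves prison without active Medicaid, or whose MOUD is paid for in another way, is scored as not linked whatever treatment they received.

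Two things are at stake. The first is the level: the published share of released people linked to MOUD would be understated, and it would not be comparable with the linkage shares from 2.9 and 2.12. The second is interpretation: a community's rate could rise or fall because Medicaid activation at release changed, with no change in MOUD. As defined, 2.10 cannot separate the two.

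**Working it through.** **Is 2.10 an exception?** I compared the denominators of the Appendix A outcomes that are measured from Medicaid claims. Outcomes 2.4, 2.5.2 to 2.5.4, 2.6, 2.7.2 to 2.7.5, 2.9, 2.12, 2.15 and the 4.x series all restrict the denominator to Medicaid beneficiaries or enrollees. Outcome 2.7.4 also requires continuous eligibility over its observation window. Outcome 2.10 alone has no such restriction.

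**Is there a stated figure to reproduce?** No. Neither document gives a linkage rate, an enrolment share, a number released or a power figure for 2.10. Every value below is an assumption.

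**Level of the rate.** Let r be the true linkage proportion and v the share of released people whose MOUD would show in Medicaid claims. If r is the same with and without Medicaid,

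observed rate = r × v, so observed ÷ true = v.

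With r = 0.20 assumed:

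| v | observed rate, all released | shortfall | rate with an enrollee denominator |
|---|---|---|---|
| 1.0 | 0.20 | 0% | 0.20 |
| 0.9 | 0.18 | 10% | 0.20 |
| 0.8 | 0.16 | 20% | 0.20 |
| 0.7 | 0.14 | 30% | 0.20 |
| 0.6 | 0.12 | 40% | 0.20 |
| 0.5 | 0.10 | 50% | 0.20 |

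The shortfall depends on equal uptake. If people without Medicaid have lower true uptake it is smaller, and if none of them receives MOUD it is zero. If their uptake is higher, it is larger.

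**Arm comparison.** With shares v1 and v2 in Waves 1 and 2,

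observed rate ratio = true rate ratio × (v1 ÷ v2).

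With a true ratio of 1.00 and v2 = 0.70:

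| v1 | observed ratio |
|---|---|
| 0.60 | 0.60 ÷ 0.70 = 0.86 |
| 0.65 | 0.65 ÷ 0.70 = 0.93 |
| 0.70 | 1.00 |
| 0.75 | 0.75 ÷ 0.70 = 1.07 |
| 0.80 | 0.80 ÷ 0.70 = 1.14 |
| 0.90 | 0.90 ÷ 0.70 = 1.29 |

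Equal shares cancel, and unequal shares can push the ratio either way. With a true ratio of 1.25, the observed ratio would be 1.25 × 0.80 ÷ 0.70 = 1.43 or 1.25 × 0.60 ÷ 0.70 = 1.07.

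**Could the shares differ by wave?** The documents allow a route in each direction, both by inference. Protocol 6.1.1.4 requires techniques that link high-risk people to services and names release from institutions as a risk factor. If that work brought help with coverage, it would raise v1. The same section allows study funds to pay for treatment staff or medication. MOUD funded that way might produce no claim, which would lower v1.

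**The case against.** A reader might infer that 2.10 will show a spurious benefit of the intervention. The documents do not support that. Randomisation is stratified by state (Protocol 4.1.4). The secondary models adjust for research site and for each community's own baseline level of the outcome (Protocol 9.4.3), so chance and long-standing differences in enrolment are reduced. No section I found lists Medicaid enrolment as an intervention strategy, and study-funded MOUD could bias the ratio downward. What stands is narrower: a change in visibility caused by the intervention would not cancel, and its sign is unknown.

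It can also be said that the all-released denominator is the safer one. Enrolment after release is post-randomisation. Requiring coverage through day 14 or day 28 would also drop people who lose it in the window, possibly including those who die or are reincarcerated. This objection is sound. It is a reason to keep the all-released rate in view and not to require continued enrolment. It does not make that rate a correct linkage proportion.

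The contrast with 2.9 has a limit. There the index overdose itself comes from claims, so an enrollee denominator follows from the sampling frame, whereas 2.10 starts from corrections releases. A different denominator is therefore understandable, but the numerator still cannot see all of it.

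Three further points are fair. Protocol 10.1.8.1 calls the Appendix A entries brief descriptions, and SAP 6.1 cites a separate technical specifications document that was not available here and may restrict the cohort. The offset rule in 9.4.3 follows a sentence about H2 to H4, so applying it to 2.10 is a reasonable inference and not an explicit statement. The evaluation period ended in June 2022, so any new rate is a late addition and should be labelled as one.

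**Conclusion.** The point holds for the level of the rate. As Appendix A is written, released people without active Medicaid can never count as linked, and the reported proportion is too low by roughly the unenrolled share: 10% to 50% for assumed enrolment of 90% down to 50%. This rests on equal MOUD uptake with and without Medicaid and on enrollees' MOUD being billed to Medicaid. The documents supply no enrolment share.

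For the arm comparison, the conclusion is conditional. The ratio is distorted only if visibility differs by wave, by the factor v1 ÷ v2, and the direction cannot be stated in advance. Nothing in the documents shows that such a difference exists.

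A reader might also infer that the trial's main findings are in doubt. They are not. Table 2 lists 2.10 among the other secondary outcomes with no associated hypothesis, and the SAP was narrowed to opioid overdose deaths (SAP 1.3, version 1.1) and does not analyse 2.10.

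**What to change.** In Protocol Appendix A, outcome 2.10:

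1. Add a linkage rate with numerator and denominator both limited to released people who have full-benefit Medicaid at release or within a fixed few days after it. Do not require continued enrolment to day 14 or day 28.
2. Report it side by side with the all-released rate, and label the latter as Medicaid-observed linkage.
3. Report the enrolled share by wave, so that linkage and enrolment can be told apart.
4. Where all-payer, OASAS, BSAS or Massachusetts PDMP data exist, use them in a sensitivity analysis.
5. If the technical specifications already restrict the cohort, align Appendix A with them.

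The cost is a wording change and one merge with the eligibility files that Table 2 already lists. The downside is a smaller denominator conditioned on enrolment after randomisation, which is why both rates and the enrolled share are shown. The added rate would still miss MOUD that enrollees obtain outside Medicaid, and it would slightly understate linkage for those who lose coverage within the window.
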